8.1.8.2 Adverse Events

Adverse events (AEs) will be coded using the Medical Dictionary for Regulatory Activities (MedDRA) dictionary. Treatment-emergent adverse events (TEAEs) will be summarized for each treatment group. TEAEs are defined as AEs with a start date on or after the first dose of the study drug and within 30 days of the last dose of the study drug. AEs starting more than 30 days following discontinuation of the study drug will not be included in the summaries of TEAEs. AEs starting more than 30 days following discontinuation of the study drug will be summarized separately as Post-Treatment AEs.

When summarizing TEAEs by relationship or severity, if a subject has an event with unknown severity or relationship, then the subject will be counted in the severity/relationship category of "unknown," even if the subject has a second occurrence of the same event with a severity/relationship present. The only exception is if the subject has a second occurrence of the same event with the most extreme severity (i.e., "severe") or a relationship category of "reasonable possibility." In this case, the subject will be counted under these most extreme severity/relationship categories.

Frequencies and percentages of subjects with TEAEs will be calculated for each treatment group as follows:

- Any event
- By system organ class, and preferred term
- By system organ class, preferred term and maximum relationship
- By system organ class, preferred term and maximum severity

- Any event and by system organ class and preferred term for events resulting in study drug discontinuation
- Any event and by system organ class and preferred term for serious events
- Any event and preferred term for AESI's (e.g., hypoestrogenic adverse events)

The Post-Treatment AEs will be summarized in a similar manner as the TEAEs described above.

8.1.8.3 Analysis of Laboratory Data and Vital Signs

[figure not shown]
Changes from the baseline to each visit in continuous laboratory and vital sign parameters will be summarized by treatment group. Treatment group differences for changes from baseline will be analyzed using a one-way ANOVA with treatment as the main effect.

Laboratory values will be categorized as low, normal or high based on normal ranges of the central laboratory used in this study. Low or high laboratory values will be flagged in the data listings.

Analysis details will be specified in the SAP.

8.1.8.4 Bone Mineral Density

The within-group percent change from baseline to Month 6 in BMD will be summarized for each treatment group with mean, standard deviation, median and two-sided 95% confidence interval. The between-group differences in percent change from baseline to Month 6 in BMD will be summarized with mean and standard error. The percent change from baseline to Month 6 in BMD will be compared between each elagolix treatment group and the placebo group as well as between the elagolix 300 mg BID group and the elagolix 300 mg BID plus E2/NETA group using ANCOVA with treatment as the main effect and baseline BMD as a covariate. Two-sided 95% confidence intervals will be constructed for the between-group differences in percent change from baseline to Month 6 in BMD.

The number and percentage of subjects with categorized percent change from baseline in BMD (e.g., $\leq -3\%$, $\leq -5\%$, or $\leq -8\%$) will be summarized for each treatment group and comparison between each elagolix treatment group and the placebo group as well as between the elagolix 300 mg BID group and the elagolix 300 mg BID plus E2/NETA group will be made.

In addition, to evaluate BMD change, the percent change from baseline to Month 6 in the Treatment Period using aggregated data from two pivotal studies (Studies M12-815 and M12-817) will be compared between each elagolix treatment group and the placebo group as well as between the elagolix 300 mg BID group and the elagolix 300 mg BID plus E2/NETA group using ANCOVA with treatment as the main effect and baseline BMD as a covariate. Two-sided 95% confidence intervals will be constructed for the differences in percent change from baseline to Month 6 in BMD.

Analysis details will be specified in the SAP.

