All randomized subjects who took at least one dose of the study drug will be included in the safety analyses. The number and percentage of subjects having adverse events will be tabulated by primary SOC and MedDRA Preferred Term with a breakdown by treatment group. Hematology, chemistry, urinalysis, lipid panel, vital signs and endometrial biopsy variables will be summarized.

Statistical Methods (Continued):

Safety (Continued):

To evaluate BMD change, the percent change from baseline to Month 6 in the Treatment Period using aggregated data from two pivotal studies (Studies M12-815 and M12-817) will be compared between each elagolix treatment group and the placebo group as well as between the elagolix 300 mg BID group and the elagolix 300 mg BID plus E2/NETA group using analysis of co-variance (ANCOVA) with treatment as the main effect and baseline BMD as a covariate. Two-sided 95% confidence intervals will be constructed for the differences in percent change from baseline to Month 6 in BMD.

Sample Size:

[figure not shown]
Approximately 400 subjects will be randomized (1:1:2) to placebo (N = 100), elagolix 300 mg BID (N = 100), or elagolix 300 mg BID plus E2/NETA (N = 200) for 24 weeks of dosing. The sample size will provide at least 90% power to detect a difference between the elagolix 300 mg BID plus E2/NETA group and the placebo group in the percentage of subjects with MBL volume < 80 mL during the Final Month (the last 28 days of treatment) and 50% or greater reduction in MBL volume from baseline to the Final Month under the assumption of responder rates being 60% and 30% for elagolix 300 mg BID plus E2/NETA and placebo, respectively.

Pharmacokinetic:

Plasma concentrations of elagolix and norethindrone will be listed for each subject by visit day and dose regimen. Pharmacokinetic data may be combined with data from other studies in women. Exposure-response analyses may be conducted as appropriate.

Pharmacodynamic:

Serum concentrations of estradiol, progesterone, FSH, and LH will be listed for each subject by visit day and dose regimen.

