The Phase 3 endometriosis clinical development program is comprised of two 6-month replicate, randomized, double-blind, placebo-controlled pivotal studies (Studies M12-665 and M12-671), each with complimentary 6-month safety/efficacy extension studies (Studies M12-667 and M12-821). The extension studies are ongoing. The primary objective of the pivotal studies are to evaluate the safety, tolerability, and efficacy, of elagolix, administered QD or BID compared to placebo, in the management of moderate to severe endometriosis-associated pain while taking into account the use of rescue analgesics. Secondary efficacy objectives include assessments of other endometriosis-related symptoms, analgesic use, as well as quality of life (QoL) endpoints. The 6-month extension studies assess the long-term safety and efficacy of elagolix for a total treatment duration of up to 12 months.

Phase 3 Clinical Development Program for Uterine Fibroids

The overall objective of the registration clinical development program is to generate requisite safety, tolerability, and efficacy data in 2 replicate 6-month Phase 3 pivotal studies and 1 safety and efficacy extension study (total 12-month treatment period) to support use of elagolix 300 mg BID with E2/NETA (estradiol 1.0 mg/norethindrone acetate 0.5 mg) for the intended indication of the chronic management of HMB associated with uterine fibroids. Furthermore, the goal is to generate data that supports long-term use with this treatment regimen.

The primary objective of these pivotal studies is to evaluate the efficacy and safety of elagolix 300 mg BID in combination with add-back therapy (E2/NETA) as compared to placebo to reduce HMB associated with uterine fibroids. Given the difficulties with extending placebo for periods beyond 6 months, the elagolix 300 mg BID alone arm serves as a reference arm, which will be useful in fully understanding the protective effects of standard dose E2/NETA on BMD over a 12-month treatment period.

Subjects who complete either pivotal study (Studies M12-815 or M12-817) will have the option to enter into the extension study (Study M12-816) to receive an additional 6 months of therapy, for a total of up to 12 months of active treatment for those randomized in the pivotal studies to active treatment and a total of 6 months of treatment for those randomized to placebo in the pivotal studies.

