11.2.4 Adenomyosis Subset

The proportion of responders and difference in proportions between each elagolix treatment group and placebo will be summarized as in the primary analysis for subjects with Baseline adenomyosis present, and repeated for the subjects with adenomyosis at any time during the Baseline or Treatment Period (see definition in Section 11.3.5.3). No statistical tests will be performed. This will be calculated using the same imputed datasets as in the primary analysis, subset for the subjects identified in the adenomyosis subset of interest.

For each of the adenomyosis subsets defined in Section 11.3.5.3, the statistical comparison between each elagolix dose group and placebo for subjects with Baseline adenomyosis present will be made using a logistic regression model including treatment as the main effect and Baseline MBL volume as a covariate in the integrated summary of efficacy (ISE) setting together data from Studies M12-815 and M12-817. The proportion of responders, difference in proportions between each elagolix treatment group and placebo and odds ratio with corresponding 95% CI, and p-values will be calculated. This will be calculated using the same imputed datasets as in the primary analysis for each respective study, subset for the subjects identified in the adenomyosis subset of interest.

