12.4.1 BMD in the Treatment Period

BMD

A continuous summary of BMD at Baseline, Between Month 3 and Month 6, Month 6, and Final Visit will be provided by treatment group. This summary will include the mean, SD, median, minimum, maximum, and first and third quartiles. This analysis will be repeated excluding subjects who switched machine manufacturer type (Lunar or Hologic), subjects with scans only on Lunar machines, and subjects with scans only on Hologic machines.

The analysis of percent change in BMD from Baseline to each relevant visit in the Treatment Period will be performed. The mean percent change in BMD from baseline to Month 6 and Final Visit during the Treatment Period will be compared between each elagolix dose group and placebo, as well as between elagolix 300 mg BID group and elagolix 300 mg BID + E2/NETA group, using ANCOVA with treatment as the main effect and Baseline value of corresponding parameter as a covariate. This analysis will be repeated excluding subjects who switched machine manufacturer type (Lunar or Hologic), subjects with scans only on Lunar machines, and subjects with scans only on Hologic machines.

The number and percentage of subjects with percent change from Baseline to Between Month 3 and Month 6, Month 6, and Final Visit in the Treatment Period in mutually exclusive categories of BMD decrease: $\leq 0\%$, $> 0\% - \leq 1.5\%$, $>1.5\% - \leq 3\%$, $> 3\% - \leq 5\%$, $> 5\% - < 8\%$, and $\geq 8\%$ will be summarized by treatment group and comparison between each elagolix dose group and placebo, as well as between elagolix 300 mg BID group and elagolix 300 mg BID + E2/NETA group, will be made using Fisher's exact test.

Z-Score and T-Score

A continuous summary of the Z-score at Baseline, Between Month 3 and Month 6, Month 6, and Final Visit will be provided by treatment group. This summary will include the mean, SD, median, minimum, maximum, and first and third quartiles. A categorical summary of Z-score will be summarized at Baseline, Between Month 3 and Month 6, Month 6, and Final Visit for the following categories: ≤ -2.0 , > -2.0 to ≤ -1.5 , > -1.5 to ≤ -1.0 , and > -1.0 for all subjects, subjects with BMD decrease $\geq 3\%$ at Month 6, and subjects with BMD decrease $< 3\%$ at Month 6, respectively. The categorical summary of worst Z-score at any time in the Treatment Period will be produced by treatment group for each anatomical region.

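### The pooled M12-815/M12-817 BMD and adenomyosis models leave out study; the effect is modest, the analyses are supportive, and one model term in each corrects it

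*Protocol*

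**What the plan says.** **Pooled BMD.** Protocol 8.1.8.4 first sets out the BMD analyses within M12-815. It then adds that the Month 6 percent change "using aggregated data from two pivotal studies (Studies M12-815 and M12-817) will be compared" for each elagolix arm against placebo and for the two elagolix arms against each other, "using ANCOVA with treatment as the main effect and baseline BMD as a covariate". The synopsis gives the same model: "using analysis of co-variance (ANCOVA) with treatment as the main effect and baseline BMD as a covariate".

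**The SAP on BMD.** The protocol leaves analysis details to the SAP. SAP 12.4.1 describes only the M12-815 comparison, "using ANCOVA with treatment as the main effect and Baseline value of corresponding parameter as a covariate". SAP 12.4 contains no pooled BMD analysis, so the protocol's two-term model is the only pooled BMD model in these documents.

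**Pooled adenomyosis.** SAP 11.2.4 keeps the M12-815 subset summary descriptive and places the testing in pooled data: a logistic regression with treatment and "Baseline MBL volume as a covariate in the integrated summary of efficacy (ISE) setting together data from Studies M12-815 and M12-817". Odds ratios, 95% confidence intervals and p-values are planned. The imputed datasets come from each study's own primary analysis.

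**The two studies.** Protocol 3.2.3 calls them "2 replicate 6-month Phase 3 pivotal studies". Protocol 8.1.3 refers to a randomization schedule belonging to M12-815. SAP 5.2 says that randomization was not stratified. Neither document names study as a covariate, stratum or interaction in a pooled model.

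**The concern.** Randomization protects comparisons made inside a trial. When two trials are stacked, study becomes a design stratum, and a model without it mixes within-study and between-study information. M12-817's schedule is not in these documents, but M12-817 is a distinct trial.

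The studies could plausibly differ:
- DXA scans use two manufacturers (Protocol 5.3.1.1). The SAP thinks this important enough to repeat its BMD analyses by machine type, and the mix may vary by study.
- Safety analyses use observed data only (SAP 12.1). Women who stop before Month 3 generally have no discontinuation DXA. Arm ratios among scanned women therefore need not match across studies.
- MRI is done in a consenting subset and overrides ultrasound when the two disagree at Baseline (SAP 11.3.5.3). MRI uptake therefore affects who enters the adenomyosis subset.

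At stake are the precision, and under some conditions the accuracy, of one supportive safety comparison, and the size of the odds ratio in one subset analysis.

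**Working it through.** **The plan's own figure.** No sample size or power is given for either pooled analysis. The stated power of at least 90% concerns the primary endpoint in M12-815 (60% v 30%, n = 200 v 100). It reproduces at 0.999, and nothing below depends on it.

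**Inputs.** M12-815 allocates 100/100/200 (Protocol 8.2). M12-817's size and allocation are not given; I assume they match, and vary this in step 3. The between-study shifts, placebo rates by study and adenomyosis prevalence are also assumptions. The spread of BMD change is back-calculated from the Phase 2b lumbar-spine categories in Protocol 3.2.2, assuming normality:
- Elagolix alone, 33% with more than 5% loss and 8% with at least 8%: SD = (8 − 5)/(1.405 − 0.440) ≈ 3.1 points.
- Elagolix plus E2/NETA, mean −0.1%. With 10.2% losing at least 3%, SD = 2.9/1.270 ≈ 2.3. With 2% losing more than 5%, SD = 4.9/2.054 ≈ 2.4.

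**1. ANCOVA standard error, in SD units.** Let d be the between-study difference in mean BMD change that remains after baseline adjustment, in residual SDs. With two equal studies, leaving study out adds d²/4 to the residual variance:

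SE ratio = √(1 + d²/4)

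| d | SE ratio |
|---|---|
| 0.25 | 1.008 |
| 0.50 | 1.031 |
| 0.75 | 1.068 |

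**2. The same in BMD points.** Pooled placebo 200 v combination 400. With study in the model, SE = SD × √(1/200 + 1/400), which is 0.208 at SD 2.4 and 0.268 at SD 3.1.

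| Study shift (points) | SE inflation, SD 3.1 to SD 2.4 |
|---|---|
| 0.5 | 0.3% to 0.5% |
| 1 | 1.3% to 2.2% |
| 2 | 5.1% to 8.3% |

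**3. ANCOVA bias.** Bias = shift × (second study's share of the active arm − its share of the placebo arm).
- Same arm ratio in both studies: the shares are equal and the bias is 0.
- Evaluable placebo:combination 100:200 in one study and 80:200 in the other: 200/400 − 80/180 = 0.056. The bias is 0.03, 0.06 or 0.11 points for shifts of 0.5, 1 or 2.
- A deliberately large case, 100:200 and 100:100: 100/300 − 100/200 = −0.167. The bias is 0.08, 0.17 or 0.33 points in absolute size.

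**4. Logistic model, balanced studies.** Take an odds ratio of 3.50 within each study, which is what 60% v 30% implies, and placebo rates of 21% and 41%.
- Active rates: 48.2% and 70.9%.
- Averages: placebo 31.0%, active 59.5%.
- Odds ratio without study: (0.5953/0.4047)/(0.31/0.69) = 3.27.

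Placebo rates of 25%/35% and 17%/48% give 3.44 and 3.00.

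The standard error does not rise as it does in the linear model. With an assumed 40 placebo and 80 active women, the SE of the log odds ratio at 21%/41% is 0.411 without study and 0.425 with it. The z statistics are ln 3.27/0.411 = 2.88 and ln 3.50/0.425 = 2.95.

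**5. Chance imbalance in the subset.** In simulated subsets drawn independently by arm and study, the between-arm difference in study share has mean zero by symmetry and these SDs:

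| Assumed adenomyosis prevalence | Expected placebo / combination | SD of share difference |
|---|---|---|
| 10% | 20 / 40 | 0.13 |
| 20% | 40 / 80 | 0.09 |
| 30% | 60 / 120 | 0.07 |

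Placebo rates of 21% and 41% differ by 0.96 on the logit scale. To first order, a one-SD imbalance moves the log odds ratio by 0.13 × 0.96 ≈ 0.12 at 10% prevalence and 0.07 × 0.96 ≈ 0.07 at 30%, in either direction.

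**The case against.** **These may be outlines.** The protocol defers BMD detail to the SAP, and SAP 11.2.4 places the adenomyosis test in an integrated summary. An integrated-analysis plan that names study may exist. This stands in part: the documents cannot show which models will finally be run. They do show the models as written, and both lack study.

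**The stakes are limited.** A reader might infer that the pooled BMD comparison carries the bone-safety conclusion for E2/NETA. The documents do not say so. Protocol 8.1.8.4 adds it to within-study analyses that have their own confidence intervals, and SAP 12.4.1 sets out the M12-815 comparisons in full, including elagolix alone against the combination. This objection stands.

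**Large shifts are unlikely.** The outcome is within-woman percent change, adjusted for baseline, in trials described as replicates. A shift of 0.75 SD is 1.8 to 2.3 points. The Phase 2b difference between elagolix alone and the combination was about 3.5 points (−3.6% v −0.1%). The lower rows of the tables are the realistic ones.

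**Bias is not shown.** A reader might infer that the pooled BMD estimate is biased. That needs evaluable arm ratios that differ between the studies, and nothing in the documents shows that they do.

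**The logistic model behaves differently.** A reader might carry the wider-error argument over to it. Step 4 shows the reverse: the SE falls slightly and the odds ratio attenuates. With balance this is non-collapsibility rather than confounding. The model without study estimates an odds ratio averaged over the two trials, and the test statistic changes little.

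**Conclusion.** The omission is real in both pooled models, and its likely effect is modest. For BMD it costs about 1% to 3% in standard error for shifts up to 0.5 SD and about 7% at 0.75 SD, assuming equal-sized studies. Bias arises only if evaluable arm ratios differ between studies. For adenomyosis the odds ratio is attenuated, for example from 3.50 to about 3.27 at the assumed placebo rates, and chance imbalance in a small subset can move it further either way.

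Both analyses are supportive. The primary endpoint, the ranked secondary endpoints and the within-study BMD analyses are untouched. The figures rest on assumed shifts, placebo rates, prevalence and M12-817 design, and on SDs back-calculated under normality. Severity is minor.

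**What to change.** Add study (M12-815 / M12-817) as a fixed factor to the pooled BMD ANCOVA and to the pooled adenomyosis logistic regression. Write the pooled BMD model, with this term, into the SAP, or name the integrated-analysis plan that governs it, because SAP 12.4 is currently silent.

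The cost is 1 df per model. A reader might think there is no downside at all. For BMD that is nearly true, but the adenomyosis subset may be small, and the extra factor could then produce sparse cells. The plan should say in advance how sparse cells will be handled.

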8.1.8.5 Post-Treatment Analysis of Menstruation

The time of the first post-treatment menses onset in days relative to the date of the last dose of the study drug will be calculated.

8.1.8.6 Endometrial Biopsy

The number and percentage of subjects in each category of endometrial biopsy result will be summarized.

8.1.8.7 Pelvic Ultrasound

The number and percentage of subjects with complex ovarian cysts > 3.5 cm, as well as the number and percentage of subjects with simple ovarian cysts > 5 cm will be summarized for each treatment group at each time point. The change from baseline to Month 6 in endometrial thickness will be summarized for each treatment group.

8.1.8.8 Columbia Suicide Severity Rating Scale (C-SSRS)

The C-SSRS will be summarized by treatment group according to published scoring guidelines.

8.1.9 Pharmacokinetic/Pharmacodynamic Analysis

Plasma concentrations of elagolix and norethindrone and serum concentrations of estradiol, progesterone, luteinizing hormone and follicle stimulating hormone will be listed for each subject by visit day and dose regimen, as applicable. Pharmacokinetic data may be combined with data from other studies in women. Exposure-response analyses may be conducted as appropriate. For example, if pharmacokinetic exposures are estimated, analyses may be conducted to assess the relationship of pharmacokinetic parameters and estradiol and progesterone concentrations, versus efficacy and safety. Additional analyses will be performed if useful and appropriate.

8.2 Determination of Sample Size

Approximately 400 subjects will be randomized in a 1:1:2 ratio to placebo (N = 100), elagolix 300 mg BID (N = 100), or elagolix 300 mg BID plus E2/NETA (N = 200). The sample size will provide at least 90% power to detect a difference between the elagolix 300 mg BID plus E2/NETA group and the placebo group in the percentage of subjects with MBL volume < 80 mL during the Final Month (the last 28 days of treatment) and 50% or greater reduction in MBL volume from baseline to the Final Month under the assumption of responder rates being 60% and 30% for elagolix 300 mg BID plus E2/NETA and placebo, respectively. The sample size determination is primarily driven by the need for a sufficient number of patients for the safety database. The above sample size was calculated using nQuery advisor 7.0.

